1. INTRODUCTION

1.1. Study Rationale

1.1.1. Amyotrophic Lateral Sclerosis

Amyotrophic lateral sclerosis (ALS) is a progressive disorder affecting the motor neurons in the brain and spinal cord, ultimately leading to paralysis and death from respiratory failure (Brooks 1996). The incidence of ALS is approximately 2/100,000, with a prevalence of only 5/100,000 due to rapid disease progression (Chiò 2013). Median age of onset is in the mid-to-late 50s, with survival variable and often dependent on phenotype (Brown 2017). Riluzole and edaravone, the two Food and Drug Administration (FDA)-approved disease-modifying medications for ALS, confer only a modest survival benefit (Miller 2012; Writing Group; Edaravone (MCI-186) ALS 19 Study Group 2017).

1.1.2. *C9orf72*-Associated ALS

An expansion of the hexanucleotide intronic repeat GGGGCC in the *C9orf72* (C9) gene was first described in 2011 and is the most common cause of familial ALS (DeJesus-Hernandez 2011; Renton 2011; Gijselinck 2012). Approximately 40-50% of all familial ALS and up to 10% of sporadic ALS cases are attributed to this repeat expansion. Patients harboring the C9 repeat expansion have an increased predilection for bulbar-onset and the coincidence of frontotemporal dysfunction (Ghasemi 2018). The proposed mechanisms by which the C9 repeat expansion causes disease are RNA and protein-mediated neurotoxicity through accumulation of dipeptide repeat proteins (DPRs) from repeat associated non-AUG (RAN) translation and RNA binding protein (eg, TDP-43) sequestration (Brown 2017). TAR DNA-binding protein 43 (TDP-43) is an RNA/DNA binding protein important to RNA-related metabolism, found within deposits or inclusion bodies in the brains and spinal cords of patients with both sporadic and familial forms of ALS and frontotemporal dementia (FTD), including individuals with *C9orf72*-associated ALS (C9ALS) (Prasad 2019; Steinacker 2016).

1.1.3. Shared Genetics and Pathology of ALS and Frontotemporal Dementia

There is increasing evidence of not only a clinical co-occurrence but a genetic overlap between ALS and FTD (Karch 2018). Multiple genes have been identified as causative for both disorders, including TARDBP, *C9orf72*, VCP, and TBK1 (Weishaupt 2016; Smith 2012). The locus of the FTD causal gene, progranulin gene (*GRN*), carries a functional single nucleotide polymorphism (SNP) (rs5848) that is linked to survival after disease onset in C9 repeat expansion carriers (van Blitterswijk 2014). Furthermore, common variants in *GRN* (██████████) were significantly associated with an earlier age of onset and a shorter survival in individuals with ALS (Sleegers 2008). These data not only indicate that progranulin (PGRN) genetic variability acts as a modifier in ALS, but a common pathway by which *C9orf72* and PGRN cause disease.

TDP-43 is an RNA/DNA binding protein important to RNA-related metabolism, found within deposits or inclusion bodies in the brain and spinal cord of patients with both sporadic and familial forms of ALS and FTD, including individuals with C9ALS (Prasad 2019; Steinacker 2016). The prevalence of TDP-43 in most forms of ALS and tau-negative FTD

([Van Mossevelde 2018](#)) suggests a pivotal pathogenic role, and thus pathways impacting TDP-43 aggregation are potential therapeutic targets in these fatal diseases ([Scotter 2015](#); [Shenouda 2018](#)).

Chronic inflammation is another common pathogenic feature seen in ALS and FTD, suggesting the importance of central nervous system (CNS) immune cells such as microglia in both diseases. *GRN* and *C9orf72* mutations are also both associated with abnormal microglial activation ([Haukedal 2019](#)). PGRN is a highly expressed protein in microglial cells, with multiple functions including modulation of inflammation ([Haukedal 2019](#)), regulation of lysosomal function ([Tanaka 2013](#)), and neurotrophic effects including preservation of neuronal survival and axonal growth ([Gass 2012](#), [De Muynck 2013](#)). PGRN deficiency results in an exaggerated inflammatory response after brain insults ([Tanaka 2013](#); [Martens 2012](#); [Yin 2010](#)).

PGRN was shown to reverse and be protective against TDP-43 pathology in preclinical studies ([Laird 2010](#); [Tauffenberger 2013](#), [Chang 2017](#); [Beel 2018](#)), which characterizes approximately 95% of all ALS cases ([Prasad 2019](#)). While loss of PGRN was found to be detrimental in multiple models of acute and chronic neurodegeneration ([Boddaert 2018](#)), overexpression of PGRN was protective. Specifically, overexpression of human PGRN was protective against TDP-43-induced axonopathy in a zebrafish model ([Laird 2010](#)). PGRN was also shown to be protective in a *C. elegans* model of TDP-43 and FUS-induced polyglutamine toxicity ([Tauffenberger 2013](#)). PGRN overexpression in TDP-43(A315T) mice reduced the levels of insoluble TDP-43, decreased the loss of large motor axon fibers, and prolonged survival by approximately 130 days ([Beel 2018](#)). These findings are consistent with Chang et. al, suggesting impaired autophagy contributes to the accumulation of TDP-43 in *GRN*^{−/−} neurons, and that PGRN can stimulate clearance of TDP-43 through autophagy ([Chang 2017](#)). In contrast, overexpression of PGRN in mutant SOD1 mice, a model of a human ALS form that is not associated with TDP-43 pathology, did not affect onset or progression of motor neuron degeneration ([Herdewyn 2013](#)), indicating that the effect of PGRN is specific to TDP-43 pathology.

1.2. Background

1.2.1. Sortilin and AL001

Human and mouse genetic studies identified the transmembrane receptor sortilin, encoded by the *SORT1* gene, as the major negative regulator of PGRN levels in plasma and the brain ([Carrasquillo 2010](#); [Hu 2010](#)). Sortilin binds PGRN and targets it for lysosomal degradation resulting in a reduction of extracellular PGRN.

AL001 is an intravenous (IV) recombinant monoclonal antibody (known as latozinemab but referred to as AL001 within the protocol) that selectively binds to human and cynomolgus monkey sortilin. Sortilin induces the degradation of PGRN ([Carrasquillo 2010](#); [Hu 2010](#)), and its blockade leads to a chronic, 2–3-fold increase in plasma and cerebrospinal fluid (CSF) levels of PGRN in cynomolgus monkeys and in healthy human volunteers. Blocking sortilin/PGRN interactions, therefore, provides a therapeutic strategy for sustaining PGRN levels in the CNS.

Sortilin is not required for PGRN signaling, as evidenced by the fact that *SORT1*-deficient neurons retain a full response to PGRN ([Gass 2012](#)), and interestingly, *SORT1* knockout is not associated with neurodegeneration ([Jansen 2007](#)).

1.2.2. Overview of Nonclinical Toxicology Studies

To support clinical studies, the toxicology of AL001 was evaluated via single- and repeat-dose preliminary and Good Laboratory Practice (GLP) repeat-dose (4-week and 26-week) IV toxicology studies in cynomolgus monkeys. Across all the dose levels assessed (up to [REDACTED] mg/kg), there were no significant toxicology findings in the nonclinical studies.

Refer to the AL001 Investigator's Brochure for additional information regarding nonclinical pharmacology, pharmacokinetic (PK), and toxicology data.

1.2.3. Overview of Clinical Studies with AL001

AL001 is currently in evaluation for the treatment of FTD with TDP-43 pathology and in C9ALS.

Study AL001-1, Phase 1 FIH Study in Healthy Volunteers and Patients with FTD

(Completed): The AL001 dose was determined based on the results from a Phase 1 dose-finding study in healthy volunteers and in patients with FTD (Study AL001-1). A total of 52 healthy volunteers received single doses of AL001 ranging from 2 mg/kg to 60 mg/kg and 12 subjects received placebo. AL001 was generally safe and well tolerated through the highest dose assessed (60 mg/kg) and demonstrated a favorable safety profile without dose-limiting toxicities or concerning apparent trends in adverse events (AEs), with a robust pharmacodynamics (PD) effect in plasma and CSF. The second part of Study AL001-1 enrolled asymptomatic FTD-*GRN* patients who received a single dose of 60 mg/kg AL001 by IV, and symptomatic FTD-*GRN* patients who received 3 doses of IV 30 mg/kg AL001 every 2 weeks. Data showed safety and tolerability, while demonstrating proof-of-mechanism of action with prolonged post-dose increase in plasma PGRN concentration.

Study AL001-2, A Phase 2 Open-Label Extension Study in Patients with FTD (Ongoing):

Study AL001-2 is evaluating the long-term safety profile of AL001 in symptomatic and asymptomatic FTD-*GRN* carriers, and in symptomatic carriers of *C9orf72* mutations causative of FTD (FTD *C9orf72*). As of 27 August 2021, a total of 16 *GRN* carriers (5 asymptomatic and 11 symptomatic with FTD) and 9 symptomatic *C9orf72* carriers with FTD have been enrolled; study AL001-2 will enroll up to 20 symptomatic FTD *C9orf72* repeat expansion carriers. The most frequently reported treatment-emergent adverse events (TEAEs) across all study populations have been fall and rash.

Study AL001-3, A Phase 3, Randomized, Double-Blind, Placebo-Controlled Study in

Patients with FTD: Study AL001-3 is evaluating the efficacy and safety of AL001 in individuals with symptomatic FTD and at-risk *GRN* mutation carriers. The study is ongoing and remains blinded. As of the 27 August 2021 data cutoff, 38 subjects have been enrolled. There have been no deaths, no drug-related SAEs, and AEs have been predominantly mild in severity. One moderate TEAE of flagellate dermatitis led to study discontinuation.

Refer to the AL001 Investigator's Brochure for additional clinical study data.

1.2.4. Rationale for the Treatment of C9ALS with AL001

The accumulation of TDP-43 is the most significant pathological finding in approximately 95% of ALS cases, such as those associated with the C9 repeat expansion (Prasad 2019). Both data from animal models and human genetics support a neuroprotective effect of increasing

extracellular PGRN levels by reducing TDP-43-associated pathology in ALS. Taken together, these findings suggest that AL001 may be a candidate therapeutic in C9ALS.

1.2.5. Dose Justification

The AL001 dose was determined based on the AL001-1 Phase 1 study results. AL001 was generally safe and well tolerated through the highest dose assessed (60 mg/kg) and demonstrated a favorable safety profile without dose-limiting adverse events (DLAEs), with a robust PD effect in plasma and CSF.

1.3. Risk/Benefit Assessment of AL001

Refer to the AL001 Investigator's Brochure for detailed information on safety profile of AL001.

1.3.1. Known Risks of the Drug Class

Immune Response: Monoclonal antibodies like AL001 may be associated with a potential immune response, such as hypersensitivity or hypersensitivity-like reactions, including severe anaphylactic reactions.

1.3.2. Risks of AL001 and AL001-ALS-201 Study Procedures and Assessments

Risks Associated with AL001-ALS-201 Study Procedures and Assessments: The study procedures and assessments to be performed are not considered to be of great burden to subjects and are not associated with high risk.

Important Identified Risks: There are no important identified risks for AL001 to date.

Serious Adverse Drug Reactions: No serious adverse drug reactions (ADRs) have been reported in completed and ongoing clinical studies with AL001 to date and there are no expected serious ADRs for AL001.

Immunogenicity: Subjects treated with AL001 have developed anti-drug antibodies (ADAs). The preliminary assessment of ADAs has not identified any associations between incident ADAs with PK, PD, or clinical safety in subjects receiving single-dose AL001 or three doses of AL001 administered every 2 weeks. Based on the current information from studies with AL001, the impact of immunogenicity on AL001 exposure, PD effects, and clinical safety do not appear consequential with short duration of exposure. However, the impact of ADAs continues to be assessed in ongoing AL001 clinical studies with longer-term exposure. An ADA assay for neutralizing antibodies to AL001 is under development. See the AL001 Investigator's Brochure for more information on immunogenicity.

Adverse Events: AL001 has been generally safe and well tolerated. There have been no deaths, no AL001-related serious adverse events (SAEs), and no AL001-related AEs leading to study discontinuation in the clinical trials of AL001 to date. AEs have been predominately mild to moderate in severity. Refer to the AL001 Investigator's Brochure for a detailed summary of AEs.

1.3.3. Potential Benefits of AL001

AL001 is a novel recombinant human monoclonal immunoglobulin G (IgG)1 antibody that blocks sortilin, decreasing the rate of PGRN clearance, and raising the concentration of PGRN. AL001 may therefore decrease the rate of neurodegeneration associated with ALS among

patients who carry *GRN* mutations. Treatment with AL001 represents a promising therapeutic strategy for patients with C9ALS and while the efficacy of treatment with AL001 is still under investigation, patients with C9ALS may benefit from participating in clinical trials of AL001, which are designed to evaluate a potential treatment for a disease for which there are inadequate treatments. Subjects will receive either AL001 or placebo in addition to their stable, standard of care treatment. All subjects will receive and potentially benefit from close medical monitoring and care from qualified professionals throughout their participation in the study.

1.3.4. Benefit-Risk Assessment for Study AL001-ALS-201 Study Subjects

Participation in Study AL001-ALS-201 offers the possibility of receiving AL001, a novel recombinant human monoclonal IgG1 antibody that blocks sortilin, for the treatment of adults with C9ALS. By blocking sortilin, decreasing the rate of PGRN clearance and therefore raising the concentration of PGRN, AL001 may decrease the rate of neurodegeneration and clinical decline associated with ALS among patients who carry *C9orf72* mutations.

More detailed information about the known and expected benefits and risks of AL001 may be found in the AL001 Investigator's Brochure.

The potential benefit of AL001 to subjects is based on the completed Phase 1 study, Study AL001-1, which demonstrated that AL001 is associated with significant and dose-dependent increases in plasma and CSF PGRN in both healthy volunteers, asymptomatic, and symptomatic carriers of *GRN* mutations causative of FTD. Of note, administration of AL001 to subjects with *GRN* mutations restored CSF and plasma PGRN levels to normal and increased plasma PGRN 2-3× in FTD subjects with *C9orf72* mutations. By blocking sortilin, decreasing the rate of PGRN clearance and therefore raising the extracellular concentration, AL001 may reduce TDP-43-associated pathology and decrease the rate of neurodegeneration and clinical decline associated with ALS among patients who carry *C9orf72* mutations (C9ALS).

Any risks to subjects in AL001-ALS-201 will be minimized through a combination of screening for appropriate eligibility criteria and rigorous safety monitoring to identify risks, as well as careful toxicity management. Adverse event and/or severe AE collection will occur up to 8 weeks after last dose of study treatment. Frequent safety monitoring will ensure that updated safety information is available in a timely manner and that any future changes to the risk/benefit profile of AL001 are appropriately reported and managed. Alector will provide careful screening, diligent monitoring, and management of patient safety throughout the course of the study.

Taking the available data on the investigational therapy together with the study design and conduct, AL001 is anticipated to be generally safe, well tolerated and provide pharmacological effect at the dose of 60 mg/kg being administered in this study. Subjects, regardless of the treatment group to which they are randomly assigned, will receive close medical monitoring and care from qualified professionals throughout their participation in the study. Periodic safety monitoring will ensure that updated safety information is available in a timely manner and that any future changes to the benefit-risk profile of AL001 are appropriately assessed. An independent data monitoring committee (iDMC) with the capability of reviewing unblinded data will provide additional oversight of the study, supplementing the Sponsor's screening, monitoring, and management of patient safety. The assessment procedures included in the clinical studies are not considered to be of great burden to patients and are not associated with high risk. Informed consent processes are intended to both (1) describe these potential benefits

and potential risks from participating in the study and (2) ensure, in accordance with local regulation, that a legally authorized representative is identified for subjects who may not have legal capacity to provide consent. Therefore, it is plausible to conclude that the anticipated benefits of participating in this study outweigh the potential risks or inconveniences.

2. OBJECTIVES AND ENDPOINTS

OBJECTIVES	ENDPOINTS	JUSTIFICATION FOR ENDPOINTS
Primary		

 • To evaluate the safety of AL001 in C9ALS • To evaluate the tolerability of AL001 in C9ALS • To evaluate changes in plasma and CSF PGRN levels after AL001 treatment • To evaluate AL001 PK parameters in serum and CSF • To evaluate ADAs to AL001 in serum 	
 • Safety: Defined as the occurrence of TEAEs, treatment-emergent SAEs, and treatment-emergent clinically significant abnormalities in clinical and laboratory values • Tolerability: Defined as the percentage of subjects who complete the trial without TEAEs leading to treatment discontinuation • PK: Serum and CSF concentrations of AL001, and PK parameters • PD: Changes from baseline in plasma and CSF levels of PGRN • Immunogenicity: Incidence of ADAs to AL001 	Safety, tolerability, immunogenicity, PK, CSF penetration of AL001, and PD have not yet been evaluated in patients with C9ALS.
Secondary		

 • To evaluate the biological activity of AL001 as measured by NfL levels in the blood and CSF 	
 • Changes in blood and CSF levels of NfL 	The level of neurofilament, a marker of neurodegeneration, is believed to be relatively stable over time and thus, a change from baseline may demonstrate biological evidence of a disease modifying effect.
Exploratory		

 • To evaluate genotype-specific effects of AL001 on PD biomarkers for common variants of GRN • To evaluate dipeptide repeat protein (DPR) levels in CSF • To evaluate the biological activity of AL001 as measured by exploratory PD biomarkers of neurodegeneration, lysosomal 	
 • Pharmacogenetic effects of AL001 with respect to the following single nucleotide polymorphisms (SNPs): rs5848, [REDACTED] [REDACTED] • Changes in CSF levels of poly (GP) DPRs • Changes in PD biomarkers of neurodegeneration, lysosomal 	These endpoints have been chosen to provide a greater understanding of ALS and may provide opportunities for identification of surrogate endpoints that are reasonably likely to predict clinical benefit and that might serve as a basis for accelerated approval in future trials.

OBJECTIVES	ENDPOINTS	JUSTIFICATION FOR ENDPOINTS

function, and glial activation in the blood, urine, and CSF
 
 ● To evaluate the effect of AL001 on clinical measures of disease progression ● To evaluate the effect of AL001 on ventilator-free survival ● To estimate correlations between fluid PD biomarkers and clinical measures of disease progression 	
function, and glial activation in the blood, urine, and CSF
 
 ● Clinical progression as measured by changes in: 
 – ALS Functional Rating Scale-Revised (ALSFRS-R) total and domain scores – Combined Assessment of Function and Survival (CAFS) – Vital capacity (VC) – ALS Cognitive Behavioral Screen (ALS-CBS) – Digital home measures of cognition and motor speech components ● Permanent assisted ventilation (PAV)-free survival ● Correlations between fluid PD biomarkers and clinical measures of disease progression 	

Abbreviations: ADA=anti-drug antibody; AE=adverse event; ALS=amyotrophic lateral sclerosis; ALS-CBS=ALS Cognitive Behavioral Screen; ALSFRS-R=ALS Functional Rating Scale-Revised; CSF=cerebrospinal fluid; DPR=dipeptide repeat protein; IV= intravenous; NfL=neurofilament light chain; PAV=permanent assisted ventilation; PGRN=progranulin; PD=pharmacodynamic; PK=pharmacokinetic; SAE=serious adverse event; SNP=single nucleotide polymorphism; TEAE=treatment-emergent adverse event; VC=vital capacity.

3. STUDY DESIGN

3.1. Overall Design

This is a Phase 2, multicenter, randomized clinical trial evaluating the safety, tolerability, and biological effect of AL001 compared to placebo in approximately 45 adults with C9ALS.

The study consists of a Screening Period (within 3 weeks prior to Day 0), a 24-week Treatment Period, and an 8-week Safety Follow-Up Period, concluding with the Study Completion Visit (8 weeks after last study drug administration).

Informed consent will be obtained prior to the conduct of any study-related procedures. Any individual who gives written informed consent to participate in the study is considered a subject in the study. Subject eligibility will be assessed at the Screening Visit and during the Screening Period. Upon determination of subject eligibility, Day 0 will occur within 3 weeks of Screening.

Subjects will be randomly assigned to receive either standard of care + AL001 or standard of care + placebo (randomized 2:1 with stratification by rs5848 genotype [CC, CT, TT]). AL001 60 mg/kg or matching placebo will be administered via IV infusion every 4 weeks for 24 weeks.

An iDMC will review the progress of the study and perform safety reviews to evaluate potential safety and tolerability issues. The iDMC will be governed by an approved charter. The roles and responsibilities of the iDMC are summarized in [Section 10.5](#).

Refer to the Schedule of Assessments ([Appendix 1](#)) for the assessments to be performed at each study visit.

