4. STUDY POPULATION

4.1. Inclusion Criteria

A prospective subject must meet all the following criteria to be eligible for study participation:

1. Diagnosis of *C9orf72*-associated ALS with both of the following:
 - a. Documentation of a clinical genetic test demonstrating the presence of a pathogenic repeat expansion in *C9orf72*
and
 - b. Must meet possible, laboratory-supported probable, probable, or definite criteria for a diagnosis of ALS by revised El Escorial criteria ([Brooks 2000](#)).
2. Age 18 or older.
3. Capable of providing informed consent at the Screening Visit and complying with study procedures throughout the study, in the investigator's opinion and at the discretion of the Medical Monitor and the study sponsor.
4. If the subject has a participating caregiver, the caregiver must live with the subject and, in the investigator's opinion, have adequate knowledge of the subject's daily activities and function; participating caregivers must sign the caregiver section of the informed consent. Not having a caregiver is not exclusionary.
5. Time since onset of muscle weakness due to ALS \leq 36 months at the time of the Screening Visit.
6. Vital capacity (VC) \geq 50% of predicted capacity at the time of the Screening Visit. Vital capacity is preferred to be measured by slow vital capacity (SVC) in clinic. If required due to pandemic-related restrictions, forced vital capacity (FVC) measured in clinic via pulmonary function laboratory may be performed at the discretion of the Medical Monitor and the study sponsor. If due to pandemic-related restrictions in clinic vital capacity is not possible, then FVC may be performed via home spirometry at the discretion of the Medical Monitor and the study sponsor.
7. Must not be taking riluzole or must be on a stable dose of riluzole for at least 30 days prior to the Screening Visit. Riluzole-naïve patients are permitted in the study.
8. Must not be taking edaravone or must have completed at least one cycle of edaravone with a plan of continuing edaravone prior to the Screening Visit. Subjects must be off cycle and at least 2 days after the last dose administration of edaravone at the time of study drug infusions. Edaravone-naïve subjects are permitted in the study.
9. At Screening, women must be non-pregnant (as demonstrated by a negative serum pregnancy test at Screening) and non-lactating, and one of the following conditions must apply:

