5.2. Dosing and Administration

Dosing solution preparation instructions will be provided separately in a Pharmacy Manual.

AL001 or placebo will be administered IV over 60 minutes (\pm 15 minutes) by trained site personnel under the supervision of the investigator or their designee. Study treatment administration will be recorded in the source documentation and in the electronic Case Report Form (eCRF).

The investigator or a qualified designee must be present during the administration of study treatment. Subjects should be monitored for at least 60 minutes post infusion for the first 2 infusions of AL001. After the first 2 infusions, post-infusion monitoring may be reduced to 30 minutes. On treatment days, subjects will be discharged after the post-infusion monitoring period and after completion of all activities scheduled for that visit day at the discretion of the investigator or qualified designee.

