⁹ Safety laboratory tests will be performed pre-infusion and include hematology (CBC with differential), complete chemistry panel (to include liver function tests), and urinalysis. Urine pregnancy test will be performed in women of childbearing potential.

¹⁰ A coagulation panel including PT/INR, aPTT is to be performed at Screening and Visit 7.

¹¹ Serum PK samples will be drawn pre-infusion on the day of the infusion visit and within 15 minutes after the end of infusion (including the line flush).

Additional serum PK samples will be collected at Visit 5 at 3 hours (\pm 90 minutes) post end of infusion. Subjects will also be required to return to the study site for the Visit 5 at 24 hours (\pm 6 hours) post end of infusion for additional serum PK samples.

¹² Biomarker samples include plasma and urine at Visits 2-10 and Early Termination. At the Screening Visit, only plasma will be collected.

¹³ Blood serum samples will be collected prior to infusion for determination of ADA. In the event of an infusion reaction, blood samples should be obtained for serum PK and ADA assessments of AL001 or placebo, and the following assessments should be performed: CRP, ferritin, tryptase, and IL-6 (at 1 to 2 hours after the IRR, then again at 48-72 hours after the IRR). Where possible, clinical laboratory samples should be drawn at the site for the central laboratory; however, local laboratories may be utilized and results assessed for safety by the investigator.

¹⁴ All women of childbearing potential will have a serum pregnancy test at Screening. Urine pregnancy tests will be performed at all subsequent visits. If a urine pregnancy test is positive, it must be confirmed by a serum pregnancy test.

¹⁵ Subjects may only undergo a LP if they have a coagulation panel and platelet count performed (using a central or local laboratory) within 4 weeks prior to the LP. If the laboratory results are abnormal and warrant repeat studies, they should be repeated within a week prior to the LP, and can be repeated at a local laboratory as needed. Lumbar puncture at Visit 8 is to be performed prior to study drug administration, and at approximately the same time of the day as the

Screening LP. The LP is to be performed after pulmonary function testing and administration of the ALSFRS-R. For subjects who are rescreened, if a LP was previously completed as part of Screening and is within 12 weeks of reconsenting, then a repeat LP is not necessary.

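### The ± 7-day windows, with no minimum interval between infusions, allow two 60 mg/kg doses 14 days apart from the second gap on; a one-sentence 21-day floor would be a cheap safeguard of modest value

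*Protocol*

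**What the plan says.** Protocol Section 3.1 sets the regimen: "AL001 60 mg/kg or matching placebo will be administered via IV infusion every 4 weeks for 24 weeks". SAP Section 2.1 counts seven doses, Visit 2 to Visit 8.

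The Schedule of Assessments (Protocol Appendix 1) places the infusions at Weeks 0, 4, 8, 12, 16, 20 and 24. Visit 2 is Day 0 without a window. Visits 3 to 8 each carry ± 7 days around the nominal week, not around the previous dose. Section 6.3 asks sites to rebook a missed visit inside its window and does not mention the previous infusion. Sections 3.1, 5.2 and 6.1 to 6.3, the Appendix 1 footnotes and Appendix 2 state no minimum interval.

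On earlier exposure, Section 1.2.3 reports healthy volunteers who "received single doses of AL001 ranging from 2 mg/kg to 60 mg/kg", asymptomatic carriers given one 60 mg/kg dose, and symptomatic carriers "who received 3 doses of IV 30 mg/kg AL001 every 2 weeks". It does not give the doses used in the two later AL001 studies. Sections 1.2.3 and 1.2.5 report no dose-limiting events up to 60 mg/kg.

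Inclusion criterion 8 constrains infusion days for edaravone users: "Subjects must be off cycle and at least 2 days after the last dose administration of edaravone at the time of study drug infusions".

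**The concern.** Because each window is tied to the calendar from Day 0, a late visit followed by an early one shortens the gap from both ends. Both visits are in window, so the short gap is not a deviation and nothing prompts the site to stop. The first gap is protected because Day 0 cannot move; the other five are not.

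Safety and tolerability are primary objectives, and Section 2 notes that they had not yet been evaluated in C9ALS. The only 2-weekly dosing that the protocol describes used half the present dose, for three infusions. At stake is an avoidable rise in peak exposure for a few subjects, which the documents neither intend nor discuss.

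**Working it through.** **1. Dose count.** 24/4 + 1 = 7, which matches the SAP and the seven infusion marks in Appendix 1.

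**2. Range of each gap.** Shortest gap = (later nominal day − 7) − (earlier nominal day + its window).

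- Visit 2 to 3: (28 − 7) − (0 + 0) = 21 days; longest (28 + 7) − 0 = 35.
- Visit 3 to 4: (56 − 7) − (28 + 7) = 14 days; longest (56 + 7) − (28 − 7) = 42. Visits 4–5, 5–6, 6–7 and 7–8 give the same.

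Example: Visit 3 on Day 35 and Visit 4 on Day 49 are both in window and 14 days apart. Two 14-day gaps cannot be consecutive; at most three of the six gaps can be 14 days (Days 0, 35, 49, 91, 105, 147, 161).

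**3. Effect on the peak.** The half-life t is assumed at 7, 14 and 21 days. Elimination is taken as first-order, infusions as instantaneous, and the first five doses as given on Days 0, 28, 56, 84 and 112. In units of one 60 mg/kg dose:

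peak after the Visit 8 dose = 1 + Σ 2^(−days since each earlier dose / t).

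For t = 14, nominal schedule (Visit 7 on Day 140, Visit 8 on Day 168): 1 + 2^−2 + 2^−4 + … + 2^−12 = 1.333. With Visit 7 on Day 147 and Visit 8 on Day 161: 1 + 2^−1 + 2^−3.5 + 2^−5.5 + 2^−7.5 + 2^−9.5 + 2^−11.5 = 1.618. Ratio 1.618/1.333 = 1.21.

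| Assumed half-life (days) | 7 | 14 | 21 |
|---|---|---|---|
| Peak, 28-day gap | 1.067 | 1.333 | 1.655 |
| Peak, 14-day gap | 1.258 | 1.618 | 1.956 |
| Ratio, 14-day to 28-day | 1.18 | 1.21 | 1.18 |
| Largest ratio with a 21-day floor (Day 140 to 161) | 1.06 | 1.10 | 1.10 |
| Peak of 30 mg/kg every 2 weeks × 3 | 0.656 | 0.875 | 1.013 |
| Nominal schedule relative to that | 1.63 | 1.52 | 1.63 |

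The fourth row is the maximum over all in-window Visit 7 and Visit 8 days at least 21 days apart. The fifth row is 0.5 × (1 + 2^(−14/t) + 2^(−28/t)).

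**4. How often.** Section 9.1 plans 30 subjects on AL001. Each has five gaps between windowed visits: 30 × 5 = 150. Visit deviations are assumed independent whole days from −7 to +7. A gap is under 21 days when the later deviation is at least 8 days below the earlier one.

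- Even over the window: (7 + 6 + 5 + 4 + 3 + 2 + 1)/15² = 28/225 = 0.1244 per gap; × 150 = about 19.
- Truncated normal, SD 3 days: 0.0314; × 150 = 4.7.
- Truncated normal, SD 2 days: 0.0038; × 150 = 0.6.

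A gap of exactly 14 days has probability 1/225 = 0.0044 if visits are even, and 0.00008 at SD 3.

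**5. If sites book from the last dose.** Neighbouring deviations then correlate positively. With an assumed correlation of 0.5 and SD 3, the SD of the difference is √(2 × 9 × 0.5) = 3. P(gap < 21 days) is then about Φ(−7.5/3) = 0.6%, or about 0.9 of 150 gaps.

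**The case against.** Nominal-week windows are a legitimate choice: they stop the schedule drifting and hold the total at seven doses. No document supports 21 days over 18 or 24 as a pharmacological threshold. That is right, and it makes this an improvement rather than an error.

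An interval rule may also exist out of sight. Section 5.3.1 refers administration instructions to the Pharmacy Manual, and under Section 5.6.1 the IRT gives dispensing instructions. Section 1.2.2 reports 4-week and 26-week repeat-dose toxicology without significant findings, but the top dose is redacted in the public text, so the margin over an 18–21% higher peak cannot be judged here. This limits how firmly the point can be put.

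Other safeguards exist: pre-infusion laboratory tests and vital signs, post-infusion observation, infusion-reaction and stopping rules, Medical Monitor review and an iDMC. They would detect or manage a problem, but none of them controls spacing.

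Finally, the floor has a cost for edaravone users, whose infusions must fall off cycle. The documents give no cycle length, so the size of that cost is unknown. This stands and is carried into the fix.

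**Conclusion.** The gap in the schedule is real: on the visible text, gaps 2 to 6 may be as short as 14 days and still comply. Closing it has modest patient-safety value. The window effect is a modelled peak 18–21% higher at the 14-day extreme, against 6–10% at most with a 21-day floor. Both rest on assumed half-lives and simple first-order elimination. The expected number of gaps under 21 days in the AL001 arm runs from under 1 to about 19, and which end applies depends on visit behaviour that the documents do not describe.

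Three stronger readings should be resisted.

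- A reader might infer that the windows nearly double exposure over earlier experience, since a 14-day gap gives 1.8–1.9 times the modelled peak of 30 mg/kg every 2 weeks × 3. The nominal schedule already gives 1.5–1.6 times; only the 18–21% is due to the windows. Contrasting 120 with 60 mg/kg over two infusions fails for the same reason: any two doses here total 120 mg/kg.
- A reader might infer harm. The documents show none.
- A reader might infer that 14-day gaps would be common. Under the assumed spreads they are rare.

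The study halted after 5 participants, not for safety reasons (SAP Section 1), and the SAP plans listings only. The value therefore lies in the protocol schedule and any reuse of it.

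**What to change.** Keep the nominal-week windows. Add one sentence to Section 5.2 and repeat it as an Appendix 1 footnote: *No infusion less than 21 days after the previous infusion.* This is the floor that the first gap already has. The sponsor should confirm the number against its own PK and toxicology data, and check that it agrees with the Pharmacy Manual and the IRT.

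Cost: after an on-time or early visit, no window days are lost. After a visit d days late (d = 1 to 7), the next visit keeps 15 − d of its 15 window days, so 8 at worst. The sponsor should check that the remaining days still allow off-cycle dosing for edaravone users; otherwise the floor could force a skipped dose or a deviation.

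The seven planned doses, sample size and SAP do not change. No new data are needed to monitor the rule: "Study treatment administration will be recorded in the source documentation" and in the eCRF (Section 5.2).
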